**TABLE 1: SCHEDULE OF STUDY PROCEDURES**

Study Phase	PreStudy Visit	Screening/ Study Visit 1 (Baseline)	Follow-up Study Visits			
Measure			V2 (3 mo)	V3 (6 mo)	V4 (9mo)	V5 (12 mo)
Informed Consent		X				
Review Inclusion/ Exclusion Criteria		X				
Demographics		X				
*SAHL		X	(X)	(X)	(X)	(X)
StimQ		X				
Poverty		X				
EI Engagement		X	X	X	X	X
EI Referral			X	X	X	X
EI Services			X	X	X	X
*Phila Exp. ACE			X	(X)	(X)	(X)
*Public Policy			X	X	X	X
*BSID-III						X

\*Philadelphia Expanded ACEs measure is administered only once throughout the duration of the study, during the 3-month follow-up survey. However, this measure may be completed during a later time-point in the event that it is not completed during the 3-month time-point.

\*Due to the interactive nature of the SAHL measure, in the event that the baseline visit must be conducted remotely, the participant will have the option of either completing the SAHL by utilizing a video conferencing application or completing the SAHL in-person at a later date. As a result, the SAHL is a baseline measure that may be completed during a subsequent follow-up visit. If a visit is conducted using a video conferencing application, we will try to use a HIPAA-compliant application licensed by CHOP (i.e., Skype, Bluejeans or WebEx).

\*Public policy changes that may impact access to services (e.g. changes in EI funding or eligibility) will be queried of EI staff throughout the study period.

\*BSID-III: In the event in-person procedures cannot take place at the time of the final study visit time-point (due to COVID-19 or other reasons) this assessment may be performed beyond the 12-month time-point, at a later date, any time before the child turns 42 months and 15 days old.

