The study research materials will consist of parent- and observer-reported instruments and EI data. Following written informed consent (which is either completed in person or remotely with the electronic REDCap e-consent process), participant caregivers will complete a baseline visit. Measures of demographic characteristics (child age, sex, race/ethnicity, family income, maternal education level, spoken language, and family structure) (Appendix 2), parental health literacy (SAHL) (Appendix 3), and the home learning environment (StimQ) (Appendix 4) will be collected at this visit. Due to the interactive nature of the SAHL measure, in the event that the baseline visit is conducted remotely, the participant will have the option of either completing the measure of parental health literacy (SAHL) remotely by utilizing a video conferencing application or completing the SAHL in-person at a later date. If a visit is conducted using a video conferencing application, we will try to use a HIPAA-compliant application licensed by CHOP (i.e., Skype, Bluejeans or WebEx). Measures of parent engagement and EI referral and service use will be collected at follow-up visits at 3, 6, 9, and 12 months. These visits will be conducted in-person, by telephone, or by email at the preference of the parent. Parents will be asked at study visits to complete the EI Engagement questionnaire, which was adapted from the CECPS and generated during a prior study (IRB 18-014884), and measures of completion of EI referrals (intake, registration, assignment of service coordinator, home visit, and MDE), eligibility for and initiation of EI services (IFSP), EI services use if eligible (number of EI service visits and whether services were completed or terminated), and use of other services (transfer to Preschool EI services, childcare or preschool enrollment). We will corroborate parent-reported visits with EI staff. Participants will also complete the Philadelphia Expanded ACE measure at one time-point throughout the study. This time-point will typically be the 3-month survey, however the measure may be administered during either the 6- 9- or 12-month follow-up survey time-points in the event that the survey is not completed during the 3-month time-point. The ACEs survey assesses for adverse events in that have already occurred in the past (i.e., childhood adverse experiences),

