## **3.2 Allocation to Treatment Groups and Blinding**

In this study, 360 eligible children will be randomized 1:1 to the FN or usual care consisting of routine Child Find procedures. We chose a randomized design, because it is most effective at guarding against bias and will ensure that patients in both arms are similar in observed and unobserved characteristics. The initial randomization will be stratified by practice site, child sex, and age group (0-<18 months old and 18-30 months old) to ensure

balance between groups. We will control post-hoc statistically for any imbalances that arise. Allocation concealment (blinding of the treatment assignment) will be implemented using sealed, opaque envelopes, along with stratification, and randomly permuted blocks of unequal sizes (to prevent providers and patients from manipulating the randomization). Treatment assignment will be done at the time of enrollment following informed consent and patients will be followed over time with measures related to EI referral completion, EI services completion, and patient engagement collected at baseline, 3, 6, 9, and 12 months as well as child developmental status around 12 months.

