### **3.4.2 Exclusion Criteria**

#### **3.4.2.1 Main RCT**

- 1) Child moves outside of Philadelphia County
- 2) Child has received EI services in the past 2 weeks
- 3) Child has HIV or congenital anomalies or genetic syndromes that place them at risk of developmental delays

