Measures of engagement will be collected at baseline and at follow-up visits every 3months, while EI referral and service use will be collected at follow-up visits every 3 months. In addition, public policy changes that may impact access to services (e.g. changes in EI funding or eligibility) will be queried of EI staff throughout the study period. The visits will be conducted by research staff blinded to randomization assignment by telephone or email at the discretion of the parent. The Client Engagement in Child Protective Services (CECPS, Appendix 1) is a validated 14-item measure of parent engagement in child welfare services and contains 4 subscales: receptivity, working relationship, buy-in, and mistrust Reliability was good ( $\alpha=0.95$  for the total score and  $\alpha=0.81-0.91$  for subscale scores), and correlation with measures of global engagement and helping relationships and personal support was moderate to strong ( $r=0.36$  to  $0.78$ ). Following discussions with the author of the CECPS (personal communication with [name]), the CECPS will be adapted for an EI population by conducting semi-structured interviews and cognitive testing with a separate group of parents previously referred to EI from one of the urban practices to identify new items and refine the wording on existing items. The adaption of the CECPS measure will be carried out as part of a separate study (IRB 18-014884). We have previously adapted an engagement measure for ADHD using a similar process (See Appendix). Parents will be asked at study visits to complete the adapted CECPS, which we are referring to as the EI Engagement questionnaire, and measures of completion of EI referrals (intake, registration, assignment of service coordinator, home visit, and MDE), eligibility for and initiation of EI services (IFSP), EI services use if eligible (number of EI service visits and duration of EI service visits), and use of other services (transfer to Preschool EI services, childcare or preschool enrollment). We will corroborate parent-reported visits with EI staff.

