## 7 STUDY INTERVENTION

### 7.1 Main RCT

#### 7.1.1 Description

With the implementation of the intervention, a modified FN model, the FNs will partner with families, engage them in the early intervention program, and provide ongoing communication with families, clinicians, and EI staff. Using data captured in the medical record, the FN will either meet with or speak with families remotely at the beginning of the study to review results of developmental screening tests and/or milestone assessments. This modified FN model process proceeds in five modules. Specifically, they will provide to families 1) education regarding knowledge of early child development, 2) information on the EI system and steps necessary to complete an EI referral, 3) brief motivation interviewing to assess families' goals and treatment preferences and level of interest in initiating EI referrals, 4) ongoing assistance to overcome barriers to completing EI referrals and maintaining EI enrollment, and 5) social work referrals in the event of family crisis or medical complexity. Specific procedures in separate modules, e.g. Early Intervention Intake Monitoring, have been manualized. The FN will contact families weekly to monthly by phone, text messaging, or email depending on family preference to monitor initiation and completion of referral steps, identify family concerns and/or barriers to referral completion, and assist families with problem-solving to identify barriers and solutions to complete EI referrals. Using email or telephone, the FN will also communicate with pediatric clinicians and EI staff to clarify treatment plans and goals and address emerging issues. A fidelity checklist developed in the pilot study will be utilized to assess self-reported task completion by the FN (0- not completed, 1- partially completed, 2- fully completed). In addition, the FN will summarize patient encounters, e.g. telephone calls with parents, in a log file. In the control arm, eligible children and their families will follow usual care procedures. As such, families are counseled by their clinicians, provided with educational handouts on development and the EI process, and referred to EI using electronic faxes from the clinic offices to the EI administrative office. EI staff then contact families by phone to initiate the EI referral process and arrange visits to complete the intake and evaluation (see Fig. 3). Families that fail to complete EI referrals and/or services in a timely manner may be dropped by EI but can be re-referred by their clinicians to complete the process later.

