ODEI Study Statistical Analyses Plan

Title: The Opening Doors to Early Intervention Study (ODEI)

NCT Number: NCT03625115

Document Date: July 3rd, 2024

ODEI Study Statistical Analyses Plan

Aim 1: To test the effectiveness of the Opening Doors to Early Intervention Program on EI service use and child developmental status among poor minority children residing in an urban community.

- a. *Hypothesis 1a:* A greater proportion of children who are randomized to the intervention will complete EI referrals than children in the control condition at 12 months.

Analysis: Chi square analysis on the difference in completion of MDE by study arm and logistic regression on the difference in MDE completion by arm, controlling for sex, age, and primary care site.

- b. *Hypothesis 1b:* Among children eligible for EI services, children randomized to the intervention will initiate EI services at a greater rate & receiving a longer duration of EI services than children in the control condition.

Analysis: Chi square test on the difference in EI service initiation by arm and logistic regression, controlled for sex, age, and primary care site. Survival analysis with a Kaplan-Meier curve of EI duration of services by arm.

- c. *Hypothesis 1c:* As a result, children who are randomized to the intervention will have more favorable developmental outcomes than children in the control condition at 12 months.

Analysis: Logistic regressions to determine the difference in cognitive and language BSID III scores by arm, controlling for sex, age, and primary care site.

Variable Definitions:

- Completion of EI Referrals: Completion of Multidisciplinary Evaluation (MDE)
- Initiating EI services: Date of first early intervention service
- Duration of EI services: The time between the EI service initiation and discharge from early intervention OR 12 months from randomization (if discharge date is unavailable)
- Developmental outcomes: Language and cognitive composite scores from BSID III assessment.

Aim 2: To assess whether parent engagement mediates the effects of the Opening Doors to Early Intervention Program.

- a. *Hypothesis 2a:* Parent engagement will mediate the association between program participation and completion of EI referrals and participation in EI services (duration).

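### The SAP does not start referral completion, service initiation or EI duration at randomisation, so events before the trial meet the definitions as written, and the protocol contradicts itself on whether EI status is recorded at baseline.

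*SAP*

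**What the plan says.** **Definitions (SAP, Aim 1, repeated under Aim 2).** Referral completion is completion of the MDE. Initiation is given as "Initiating EI services: Date of first early intervention service". Duration runs from initiation to discharge, or to 12 months from randomisation when no discharge date is available. Randomisation appears in these definitions only in that fallback end date. Hypothesis 1a adds a 12-month horizon, which is an upper limit.

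**Eligibility.** The one EI-related exclusion in Protocol 3.4.2.1 is "Child has received EI services in the past 2 weeks". No criterion mentions a previous MDE or services that ended earlier. Section 3.4.1.1 asks for a recent referral but sets no limit in days. Under Section 7.1.1, families that do not complete referrals or services in time "may be dropped by EI but can be re-referred by their clinicians to complete the process later".

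**When EI status is recorded.** The Table 1 row is "EI Referral X X X X", with its four marks under 3, 6, 9 and 12 months. Section 3.1.1 agrees: "Measures of parent engagement and EI referral and service use will be collected at follow-up visits at 3, 6, 9, and 12 months". Section 5.1.2.1 contrasts engagement, which is also taken at baseline, with the EI measures: "while EI referral and service use will be collected at follow-up visits every 3 months". The baseline visit list in Section 4.1.1 omits EI status. Section 3.2 says otherwise: "measures related to EI referral completion, EI services completion, and patient engagement collected at baseline, 3, 6, 9, and 12 months".

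**The concern.** Navigation cannot bring about an evaluation or a first service that took place before the child was randomised. If such events are counted, these children are successes in both arms whatever the intervention does. That pulls the arm differences in MDE completion (1a) and service initiation (1b) towards zero. Time before the trial can also enter EI duration. The same MDE variable is the mediator in hypothesis 2b, so its definition matters there as well.

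The protocol leaves two routes open. A child may have had an MDE or services in an earlier episode, left EI, and been re-referred. Or the MDE for the current referral may take place between the referring visit and randomisation: EI staff telephone families from the faxed referral (7.1.1), recruitment may follow the visit by telephone with a baseline visit scheduled later (3.1.1, 9.5.1), and assignment comes only after consent (3.2, 9.1.1).

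**Working it through.** **Plan's own figure.** There is none to reproduce. The 96% power in Section 6.5 is for the Bayley cognitive score; the plan states no power or precision for the EI outcomes.

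**Step 1: do the definitions and criteria exclude a pre-trial event?**

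| Event before randomisation | Excluded by eligibility? | Excluded by SAP definition? |
|---|---|---|
| EI services within 2 weeks before enrolment | Yes (3.4.2.1) | Not needed |
| EI services that ended earlier, child re-referred | No | No |
| MDE in an earlier referral | No | No |
| MDE for the current referral, before consent | No | No |

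**Step 2: dilution.** Let f be the share of each arm that already has the event, and p the rate among the rest. The observed rate is f + (1-f)p, so the difference between arms is (1-f)(p_intervention - p_control). For illustration p is 50% v 80%. These are the EI enrolment rates in Section 6.5, not MDE rates, and f is assumed.

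| f | Control | Intervention | Difference |
|---|---|---|---|
| 0 | 50.0% | 80.0% | 30.0 points |
| 5% | 0.05 + 0.95 x 0.50 = 52.5% | 0.05 + 0.95 x 0.80 = 81.0% | 28.5 points |
| 10% | 0.10 + 0.90 x 0.50 = 55.0% | 0.10 + 0.90 x 0.80 = 82.0% | 27.0 points |
| 20% | 0.20 + 0.80 x 0.50 = 60.0% | 0.20 + 0.80 x 0.80 = 84.0% | 24.0 points |

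Hypothesis 1b is restricted to EI-eligible children, so its f is the share of that group with an earlier service. The factor (1-f) applies there if that share is the same in both arms.

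**Step 3: power.** Assume two-sided alpha 0.05 (the documents do not state it) and the 130 control and 170 intervention children of Section 6.5. At 50% v 80%, power is 99.98% with f = 0, 99.9% with f = 10% and 99.7% with f = 20%. At a smaller assumed effect of 50% v 65%, it is 74%, 67% and 59%.

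**Step 4: duration.** If the first service was d months before randomisation and no discharge date exists, duration is 12 + d months; d = 6 would give 18. If the discharge on record belongs to an earlier episode, the whole duration can lie before the trial.

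**The case against.** - **Baseline status may be collected.** Section 3.2 lists the EI measures at baseline, so a reader who infers from Table 1 that EI status is simply first measured at 3 months goes too far. What the documents show is a contradiction. Resolving it in favour of Section 3.2 would still leave the SAP definitions without a start date.
- **No rule says that pre-trial events count.** Hypothesis 1a looks forward, and recruitment is tied to a new referral. This stands: counting such events is what open wording permits, not a stated instruction. But no rule excludes them either.
- **The routes may be rare.** The MDE is the last of five referral steps, and no interval from referral to MDE or to baseline is given. A family dropped before completing its earlier referral had no MDE, so re-referral alone does not prove an earlier event. An earlier MDE without services does not meet initiation. All of this stands, and it is why f cannot be estimated.
- **The pilot's 28%.** A reader might take 25 of 88 (Section 3.4) as the share with prior EI contact. Those children were removed by the 2-week exclusion, so the figure does not estimate f among children who are enrolled.
- **Consequence.** Only secondary outcomes are involved and the expected effect in 1a is dilution. At the planning rates power barely moves. This stands, although the reported effect would still be understated.

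**Conclusion.** The point holds for the wording of the definitions. An MDE or first service before randomisation meets the SAP's outcomes as written, eligibility does not rule it out, and the protocol contradicts itself on whether baseline EI status is recorded. The consequences are a shrinkage of the 1a and 1b differences by (1-f) and possible pre-trial time in duration. At an assumed f of 10%, a 30-point difference becomes 27 points. The true f is not in the documents and could be near zero.

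Two stronger inferences are not supported. One is that the result would favour an arm: with random allocation, and the same share of earlier events in both arms, the expected effect is movement towards no difference. The other is that the main result is at risk: the Bayley cognitive score does not use these definitions. The change is still worth making, because the definitions give a wrong answer for any such child and the remedy is cheap.

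**What to change.** 1. Reconcile Protocol 3.2 with Table 1 and Sections 3.1.1, 4.1.1 and 5.1.2.1 so that MDE and EI service status at baseline is recorded. Use dated agency records where they cover the period before enrolment. The protocol already obtains agency data under a signed release (3.1.1, 9.5.1) but does not say whether they reach back that far; this needs checking.
2. In the SAP, count completion as the first MDE dated after randomisation and by 12 months. Count initiation as the first EI service dated after randomisation, and start duration at that service.
3. For 1a, leave out children whose current-referral MDE predates randomisation. For 1b, leave out those whose current-episode services predate it. Because these events precede assignment, leaving the children out does not select on anything the arm could have changed. Report their number by arm, with a sensitivity analysis that keeps all randomised children.
4. Keep in children whose MDE or services belong only to an earlier, closed referral, and count only their events after randomisation.
5. Use the same MDE variable in 2b, and keep every child in the Bayley analysis.

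The cost is one schedule entry, SAP wording, a check of agency date coverage, and a somewhat smaller denominator for 1a and 1b.

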##### Secondary outcomes

Secondary outcomes include the Bayley-III language, motor, and socioemotional subscales and the binary outcomes of whether patients complete EI referrals and services at 12 months. Descriptive statistics for demographic, behavioral, and environmental characteristics measured at baseline will be examined across the two treatment groups to assess the success of the randomization. The secondary outcomes can be modeled using either a linear or logistics mixed effects model, which has similar flexibility. As a secondary analysis, we will examine differences in dosage (duration of EI service use and number of EI service visits) between intervention groups among those eligible for services. We will also examine the impact of public policy changes on the proportion eligible for EI and on the number of service visits pre- and post-change. In addition, we will examine the effects of the intervention by race/ethnicity group, sex, and age group (<18 months, >18 months) to assess for differential intervention effects.

---

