### **6.5 Sample Size, Statistical Power and Analysis Plan**

Our target sample size accounting for clustering by practice site for patients with complete 12-month follow-up is 300 participants. Assuming at least an 80% follow-up rate, the number needed to recruit to obtain this final sample size is about 360. Since a partial goal of the proposed intervention is to increase patient engagement, the rate of drop out is likely to be lower among the intervention group. If we conservatively assume that the drop-out rate among control patients is double that of patients on the intervention, the sample of patients

with complete follow-up will consist of approximately 130 control patients and 170 intervention patients.

Using the Bayley-III cognitive subscale as a primary outcome, we assert that the proposed intervention would be successful if it resulted in an increase of 3 points or more on this subscale. This is the minimal clinically significant outcome difference. Thus, based on the proposed sample size, we would obtain 96% power to detect a clinically meaningful difference in the Bayley-III cognitive scores. The power was estimated based on a simulation study that assumed that the sole impact of the intervention was on increasing enrollment into EI. Based on expected cognitive improvements due to EI found by Guralnick et al, we further assume that children who enrolled in EI had an average increase over a 12 month period of 10 points on the cognitive scale with a standard deviation of 1 point compared to patients who did not enroll. Based on these assumptions, an increase of 3 points on the cognitive scale between the intervention and control group would be the result of an increased rate of enrollment from 50% among controls to 80% among the intervention group. These rates of enrollment are consistent with rates suggested by our pilot data (Preliminary Studies Section).

**Figure 1** *Assessment of power to detect a clinically meaningful difference*

Power	n	
0.96	300	Assuming a minimal clinically significant outcome difference ( $\geq 3$ points increase in the BSID-III cognitive subscale)

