### **9.3 Confidentiality**

All data and records generated during this study will be kept confidential and in accordance with institutional policies and HIPAA on subject privacy. Participation in all aspects of the proposed study is completely voluntary. The research team will institute strict procedures to maintain confidentiality. Subjects will be assigned a unique identification code that will be used as the sole identifier. The data will only be shared with the investigative team during the implementation of the study and results will only be presented in aggregate form. Any results obtained cannot be related to the original source, so no results would be provided to the patient, healthcare provider, or insurance provider, except for the results of EI referrals, EI eligibility, and EI services which are part of the family navigator intervention which will be shared with clinicians and EI staff involved in the care of study participants. All study information will be maintained on a secure password-protected server with regular backup. Per standard NIH guidelines, a Certificate of Confidentiality (CoC) will be automatically generated for this NIH-funded study.

Throughout the study, the Philadelphia Infant Toddler Early Intervention data will be shared with the Study Investigators. Additionally, any necessary study data will be transmitted accordingly to Clinicaltrials.gov.

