Analysis: Test the association between study arm at 3 months and EI referral completion and the association between EI parent engagement at 3 months (mediator) and EI referral completion. If both associations are significant, complete a mediation analysis of the association between study arm and completion of EI referrals, mediated by parent EI engagement.

- b. *Hypothesis 2b:* Completion of EI referrals and participation in EI services (dosage) will mediate the association between program participation (duration), parent engagement, and child developmental status

Analysis of EI referral completion and child development status: Test the association between EI engagement at 3 months and Bayley language & cognitive T scores and the association between MDE completion (mediator) and EI engagement at 3 months. If both associations are significant, complete a mediation analysis of the association between EI engagement at 3 months and Bayley language and cognitive T scores, mediated by EI referral completion.

Analysis of program participation and child development scores: Test the association between program participation and Bayley language & cognitive T scores and the association between referral completion (mediator) and program participation. If both associations are significant,

ODEI Study Statistical Analyses Plan

complete a mediation analysis of the association between program duration and Bayley language and cognitive T scores, mediated by referral completion.

Variable Definitions:

- Program participation: participation in ODEI intervention
- Completion of EI Referrals: Completion of Multidisciplinary Evaluation (MDE)
- Initiating EI services: Date of first early intervention service
- Duration of EI services: The time between the EI service initiation and discharge from early intervention OR 12 months from randomization (if discharge date is unavailable)
- Developmental outcomes: Language and cognitive composite scores from BSID III assessment.
- Parent engagement: total score from 2 subscales on parent engagement (Buy-In/Receptivity to EI and Advocacy/Navigating the EI Process)

Aim 3: To explore whether the home learning environment, parental health literacy, or poverty moderate the effects of the Opening Doors to Early Intervention Program on child developmental status.

a. *Aim 3a:* To explore whether differences in developmental scores between intervention and control groups varies by the richness of home learning environment

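### The SAP's EI duration rule applies the 12-month limit only to children without a discharge date, so late discharges count in full while children still in service or of unknown status end at month 12

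*SAP*

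**What the plan says.** The SAP's variable definitions under Aim 1, repeated word for word under Aim 2, define the duration of EI service as "The time between the EI service initiation and discharge from early intervention OR 12 months from randomization (if discharge date is unavailable". The clock starts at first service: "Initiating EI services: Date of first early intervention service". Hypothesis 1b expects children in the intervention arm to be "receiving a longer duration of EI services than children in the control condition", and the only analysis named for that part is "Survival analysis with a Kaplan-Meier curve of EI duration of services by arm". The SAP does not say which outcome is the event, whether the month-12 substitute is a censoring time, or when records are extracted.

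The protocol (6.4.2.1, Secondary outcomes) lists, as a secondary analysis, "differences in dosage (duration of EI service use and number of EI service visits) between intervention groups" but does not define duration. Section 9.1.1 gives a 12-month participation period. Section 9.3 says of the county agency's records: "Throughout the study, the Philadelphia Infant Toddler Early Intervention data will be shared with the Study Investigators". No cut-off per child is stated.

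**The concern.** The rule does not take the earlier of discharge and month 12. It uses the discharge date whenever one exists, however late, and falls back on month 12 only when none does. This causes two problems.

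- **Two horizons in one variable.** Whether a child is followed past month 12 depends on whether that child has already been discharged. Censoring then depends on the outcome being measured.
- **Unknown treated as served.** A missing discharge date can mean that the child is still in service, or that the child stopped and no end date was obtained. Both are carried to month 12.

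At stake is the duration half of Hypothesis 1b, for which the Kaplan-Meier curve is the only stated analysis. Two analysts could draw different curves from the same records.

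**Working it through.** The documents give no expected duration, power or event rate for this outcome, so there is no stated figure to reproduce. All dates, hazards and missing shares below are assumptions.

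**1. The rule applied to single children** (duration = discharge month, or 12 if none, minus start month):

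- Start month 2, discharged month 15: 15 − 2 = 13 months (true 13).
- Start month 2, still in service at month 20, no discharge date: 12 − 2 = 10 months (true at least 18).
- Start month 2, stopped month 4, no discharge date: 12 − 2 = 10 months (true 2).
- First service month 13, no discharge date: 12 − 13 = −1 month.

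Read as plain durations, the second child was served longer than the first but scores 3 months less. The third ties with the second.

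**2. The curve past month 12, with month 12 treated as censoring.** If service starts after randomisation, every child without a discharge date leaves the risk set by service month 12. Any curve beyond that point is made up only of known discharges, so it ends at zero in both arms whatever the truth.

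To illustrate, assume service starts at month 2, hazards of 0.06 (control) and 0.03 (intervention) per month, and extraction at service month E. Then, for t between 10 and E:

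rule curve at t = S(10) × [S(t) − S(E)] / [S(10) − S(E)], where S(t) = exp(−hazard × t).

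Extraction 30 months after randomisation (E = 28), t = 18:

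- Control: 0.549 × (0.340 − 0.186) / (0.549 − 0.186) = 0.23; true 0.34.
- Intervention: 0.741 × (0.583 − 0.432) / (0.741 − 0.432) = 0.36; true 0.58.
- Arm difference: 13 points instead of 24.

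Extraction at month 24 (E = 22), t = 18:

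- Control: 0.549 × (0.340 − 0.267) / (0.549 − 0.267) = 0.14.
- Intervention: 0.741 × (0.583 − 0.517) / (0.741 − 0.517) = 0.22.
- Arm difference: 8 points instead of 24.

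Up to service month 10 the rule's curve equals the truth in this setting (0.55 and 0.74).

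**3. How far the late-extract figure depends on the model.** Exponential discharge leaves 19% (control) and 43% (intervention) in service 30 months after randomisation. Protocol 3.4 says children over 30 months old are already moving to Preschool EI. Adding an assumed exit at 36 months of age and repeating the month-30 extract by simulation gives:

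- Entry ages uniform from 0 to 30 months: the true difference at service month 18 is about 13 points and the rule gives about 11.
- Entry ages 6 to 30 months: nobody is still in service at extraction and the distortion is zero.

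**4. Children who stopped with no recorded end date.** Let m be the share of true stops without a discharge date. At service month 10 (month 12 for a month-2 start):

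retention under the rule = S(10) + [1 − S(10)] × m.

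- Control, m = 0.22: 0.549 + 0.451 × 0.22 = 0.65; true 0.55.
- Intervention, m = 0.11: 0.741 + 0.259 × 0.11 = 0.77; true 0.74.
- Arm difference: 12 points instead of 19.
- At a quarter of those shares (0.055 and 0.0275): 0.57 and 0.75, a difference of 17 points.

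The 22% and 11% come from Protocol 6.5: 360 − 300 = 60 lost, split 2:1 over 180 per arm, gives 40/180 and 20/180. They are borrowed only to set a scale, because study loss is not the same as a missing agency date.

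**The case against.** The case against has real force.

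- **Kaplan-Meier normally censors an undischarged child.** A value of 10 months is then a lower bound, not a score. This stands for the early curve. With equal starts there is no error up to service month 10, and with starts spread over months 1 to 4 the error there is about 1 percentage point. It does not cure the later curve, and the SAP does not state the censoring.
- **Records may be cut at month 12.** Protocol 9.3 is a confidentiality statement and does not say that later discharges are collected. If each child's records stop at month 12, late discharges become unavailable and the first problem disappears. This stands as a condition.
- **The rule does not always order children worse than a cap.** In simulated pairs (starts at months 1 to 4) with extraction at month 24 and mean duration 8 months, it misorders 3.5% against 5.4% for a month-12 cap. At mean 18 months it is worse, 21.9% against 18.4%.

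A reader might also infer more than the documents support:

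- **That the arm difference is roughly halved, from 24 points to 13.** This needs long service with no age exit and a reading at service month 18. Step 3 shows that it nearly vanishes for a late extract once an age exit is assumed.
- **That control mean duration is inflated by 0.4 to 1.6 months relative to intervention.** This comes from (difference in loss) × (10 − true months): 0.111 × 4 = 0.44 up to 0.222 × 7 = 1.56, the larger loss gap being 50/180 − 10/180 from the 130 and 170 completers. It rests on "If we conservatively assume that the drop-out rate among control patients is double that of patients on the intervention", which concerns study follow-up. EI data come from the county (3.1.1) under a release signed at baseline (9.5.1), and EI may itself drop families (7.1.1), so an end date may exist. The SAP also names no comparison of means.
- **That the mediation result for Hypothesis 2a is distorted.** The hypothesis names duration, but its written analysis uses referral completion only.

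**Conclusion.** The concern holds as a fault in a stated rule, with limited reach. As written, known discharges after month 12 are kept while all other children end at month 12, and unknown service is counted as service. No other section resolves this.

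The first effect depends on when records are drawn: none at month 12, potentially large at intermediate extracts, and small once nearly all children have been discharged. The second depends on the share of missing county discharge dates, which the documents do not give. In the illustration it takes between about 2 and 7 points off a 19-point difference. It narrows the arm difference if such gaps are commoner in control.

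Duration is a secondary analysis and the Bayley cognitive primary outcome is not touched, so this should be fixed but does not threaten the trial's main conclusion.

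**What to change.** Reword both variable definitions and the Hypothesis 1b analysis:

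- End the clock, for every child, at the earlier of discharge and 12 months from randomisation.
- Count discharge by month 12 as the event.
- Censor at month 12 any child whom agency records or the parent show to be in service then.
- Censor a child of unknown status at the last documented service date. Because such censoring may be informative, add a sensitivity analysis that counts these children as discharged on that date.
- State that a child whose first service falls after month 12 contributes no duration, which removes negative values.

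The cost is SAP wording and recoding of dates already held. The downside is that discharge information after month 12 is not used in this analysis. Reporting the number of unknown-status children by arm would show how much the second problem matters.
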